The participant and LAR/study partner returns to the research unit, in a fasting state (nothing to eat/drink, except water, for at least eight (8) hours before visit), 7-14 days after the LP to undergo reassessment of willingness to participate in the study and 12-week post-treatment measures, including vitals, weight, concomitant medication, history and physical, fasting safety labs (CBC, CMP, lipid panel, HbA1c, and urinalysis)) as well as:

- Provision of a snack
- Cognitive test battery & Questionnaires, including CDR plus all assessments listed in Visit 3
- Physical functional performance (same as Visit 3)
- Final AE review, instructions for future AD follow up and study staff enters disenrollment note.

The estimated duration of this visit is 3.5 hours.

A Summary Visit Schedule Table is shown on the following page(s).

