1.4. Dose Rationale and Risk/Benefits

Eligible participants will be treated with 1 mg of RAPA daily for 8 consecutive weeks. The most common adverse events include mucositis, stomatitis, diarrhea, nausea, and acneiform rash. Pneumonitis, the most serious potential adverse event, occurs in \leq 1-5% of cases, typically after prolonged drug exposure (\geq six months). In our recent clinical trial of elderly adults receiving 1mg RAPA daily, the same dosage to be used in this proposal, no serious adverse events occurred¹⁶. The reported adverse events were limited to facial rash (N=1), stomatitis (N=1; 1 on placebo and 1 on RAPA), and gastrointestinal distress (N=2).

The study will consist of a screening/baseline period of up to 30 days pre-study drug, with a 56-day (\pm 3 day) treatment period, and a post-intervention visit for study outcomes on final day of dosing and up to +14 days. The study duration is not expected to exceed 18 weeks for participants.

2. Study Objective

The objective of the study is to assess the degree of central nervous system penetration of orally administered RAPA treatment using collecting cerebral spinal fluid (CSF), and begin collecting initial data on safety, tolerability, target engagement, AD-related markers, and AD-relevant outcomes for future trials.

3. Study Design

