- Live vaccinations: Avoid co-administration
- b) Blood withdrawal. (To minimize these risks a qualified phlebotomist will perform venipunctures.)
- Pain, bleeding, bruising, or swelling at the site of the needle stick
- Hematoma
- Nerve damage
- Infection
- Fainting or light-headedness

This study may include genetic testing. Genetic information is unique to each individual and could potentially be used to discover possible changes in a person's future health status or life expectancy, or that of his/her children and family members. Even though the results of genetic testing cannot be linked to an individual, it is possible that people of specific ethnic backgrounds may be found to be at more risk for certain diseases based on future genetic research and this information might harm the individual in the future as a member of the group.

c) Cognitive Assessment and Semi-structured Interviews/Questionnaires

- Psychosocial embarrassment, discomfort or anxiety upon testing memory and thinking
- Patient or Study Partner-Reported Outcomes include questionnaires related to AD symptoms, cognition, sleep, and mood scales.
- d) Lumbar Puncture. (To minimize these risks, a qualified provider specifically trained in the procedure will perform the lumbar puncture.)
- Temporary pain and discomfort in the back.
- Headache.
- Persistent low-pressure headache due to leakage of CSF. If this headache persists, it may require additional treatment. Uncommonly, a blood patch (injection of some of participant blood into the lumbar puncture site to patch the CSF leak) may be required.
- Infection
- Damage to nerves in the back
- Bleeding into the CSF space
- Allergic reaction to the local anesthetic (lidocaine) used for the lumbar puncture, such as swelling or rash at the puncture site.

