Research labs (blood and CSF) will also be banked for future analyses, including possible genetic analyses. Before all study procedures, researchers will assess study participants' willingness to continue their study participation with direct inquiry to the study participant and LAR (if applicable). If there is any indication of diminished capacity or significant cognitive changes (i.e. observed by research staff or reported by family members), the researchers will evaluate the participant's current capacity to consent using a standardized instrument as described under Visit 1 (if the participant originally was deemed to have capacity to consent) or evaluate assent and surrogate consent (if the participant originally was deemed to lack capacity to consent).

Visit 2 is estimated to require up to 3 hours, including at least 30 minutes rest following the procedure. If indicated due to obesity, arthritis, scoliosis or any other condition that makes it difficult to identify the correct insertion point on the lumbar spine, the lumbar puncture will be completed with fluoroscopy. This procedure will occur in room RII 1.326 using a c-arm machine that has been inspected by the UT Radiation Safety Office. This room is shielded, and the procedure will be conducted by a board certified neuroradiologist who has received extensive training in the use of fluoroscopy for LPs. Refer to Standard Operating Procedures for more details about the lumbar puncture procedure.

(i) Lumbar puncture (LP) to acquire CSF (up to 30m volume)

- CSF: CSF will be separated into aliquots and frozen. See Analyses below.
- (ii) Blood draw 60mL volume for RAPA/S6k1-P levels, AD markers, proinflammatory and other relevant analytes.
 - Blood: Blood will be separated into aliquots for analysis by UTHealth Biggs Institute and Department of Cell Systems and Anatomy as follows:
 - o 40ml volume of whole blood, separated into 8 vials
 - 2ml volume of whole blood, separated into three aliquots
 - Separated from 18 of whole blood, 8-12ml of serum (0.2-0.5ml aliquots) and 6-8ml of plasma (0.2-.0.5ml aliquots)

Analyses.

CSF:

CSF will be separated into aliquots and frozen. (i) Aliquots will be analyzed by the Pharmacology Core facility using HPLC/MS chromatography; (ii) ELISA or Simoa HD-1 Analyzer for AD and pro-inflammatory markers to be performed by UT Health (Biggs Institute and Department of Cell Systems and Anatomy).

Blood:

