Blood, apportioned as described above, will separated into aliquots and frozen. i) Aliquots will be analyzed by the Pharmacology Core facility using HPLC/MS chromatography; (ii) ELISA, Luminex-based assays, and/or

Simoa HD-1 Analyzer for AD and pro-inflammatory markers performed by UT Health (Biggs Institute and Department of Cell Systems and Anatomy).

Confirm scheduling of Visit 3. Within one to two business days of Visit 3, research staff may call the study participant and/or LAR/study partner to confirm the appointment and complete COVID-19 symptom and exposure telephone assessment.

6.3. Visit 3a – Baseline Measurements Part II (within 30 days of Visit 2) and Visit 3b - COVID-19 testing (within 72 hrs of Visit 4).

Within 30 days of the Visit 2, enrolled subjects will be asked to return to the research unit with LAR for Visit 3a. Examination and activities during this visit include reassessment of willingness to participate in the study (as described under Visit 1), vital signs, concomitant medication, and adverse event review, with the following measures:

(i) Cognitive examination (1.5 hours):

- Montreal Cognitive Assessment (MoCA)
- Hopkins Verbal Learning Test Revised (HVLT-R)
- Craft Stories
- Benson Figure Copy and Delayed Recall
- Number Span Test
- Trail Making Test Parts A&B
- Phonemic Fluency
- Semantic Fluency
- Multilingual Naming Test (MINT)
- Hayling

(ii) Participant-Reported (GDS) and Informant-Reported (FAQ, NPI)

(iii)Functional and physical performance measure (1 hour):

- Electronic gait mapping under single and dual-task conditions
- grip strength

For added safety, approximately 1-2 business days before starting the drug intervention (Visit 4), participants will be asked to return for Visit 3b and tested for SARS CoV-2 with a nasopharyngeal swab for rRT-PCR (Real-time reverse transcriptase–polymerase chain reaction) analysis. Research funds will pay for the testing.. If a participant tests positive, the investigator will refer the subject to their primary care physician for medical care. Visit 3b is estimated to require 30 minutes.

Visit 3a is estimated to require 3 hours. Confirm scheduling of Visit 4. Within one to two business days of Visit 4, research staff may call the study participant and/or LAR/study partner to confirm the appointment. The COVID-19 symptom and exposure telephone assessment may be completed either at Visit 3a or at time of Visit 4 scheduling confirmation, within one-two business days of Visit 4.

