**COVID testing 24-72 hours prior to drug dispensing visit; COVID symptom and exposure assessment 24-72 hours prior to study visits; COVID testing may be repeated in event participant shows signs or symptoms of COVID-19 or, if positive, until a negative test is achieved

*At visit 7, all remaining supply of RAPA should be returned to the study staff for a final drug accountability check.

***CDR will only be repeated at visit 4 if visit 1 was conducted more than 60 days prior.

7. Statistical Plan

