7.2. Statistical Methods

Analytical Approach.

Similar to an early phase 2 trial, we seek preliminary evidence of drug safety and tolerability with estimation of pre/post differences in a pertinent laboratory values and adverse event occurrences. We will report changes in post-intervention laboratory values relative baseline with the 95% confidence interval. Experimental results will be expressed as means \pm SE. Comparisons of means between pre/post evaluations will be done by regression using the intent to treat principle defined above. Given the small sample size, there are no plans for interim analyses.

8. Safety and Adverse Events

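### The baseline Aim 4 battery (Visit 3a) has no minimum interval after the first lumbar puncture, while the same battery at Visit 8 must wait at least 7 days after the second

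*Combined protocol and SAP*

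**What the plan says.** The first LP is at Visit 2 (Section 6.2). The only recovery time stated there is within the visit itself: "Visit 2 is estimated to require up to 3 hours, including at least 30 minutes rest following the procedure". The baseline Aim 4 battery follows at Visit 3a. Section 6.3 says "Within 30 days of the Visit 2, enrolled subjects will be asked to return to the research unit with LAR for Visit 3a", and the table in Section 6.9 likewise gives only an upper limit of 30 days after Visit 2.

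The second LP and the final dose are both at Visit 7 (Section 6.7). The same battery, with the CDR added, is repeated at Visit 8. Section 6.8 ties that visit to the LP: "7-14 days after the LP to undergo reassessment of willingness to participate in the study and 12-week post-treatment measures". The section heading and the table give the same 7-14 days after Visit 7.

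Section 3.3(d) lists headache, back pain and "Persistent low-pressure headache due to leakage of CSF" among the risks of LP. For the analysis, Section 7.2 says "Comparisons of means between pre/post evaluations will be done by regression". It plans no check on the time between LP and testing.

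**The concern.** The trial has one arm, so anything that makes the two test occasions differ, other than treatment, goes straight into the pre/post change. A recent LP is one such factor, and the protocol controls it on one side only. A participant may be tested at baseline the day after an LP, yet cannot be tested within a week of one after treatment. If headache or back pain lowers performance at baseline, recovery from the LP would look like benefit from the drug.

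The outcomes exposed are those the participant performs or reports: the cognitive tests, gait, grip strength and the GDS. The FAQ and NPI come from the informant and are less directly exposed. Aim 4 is meant to supply early data for a larger Phase 2 trial, so a shift caused by visit timing could be carried into its planning.

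The twelve-week label on the Visit 8 measures adds a smaller difficulty. It does not match an 8-week course followed by a visit 1-2 weeks later, and a reader cannot tell from it that Aim 4 is measured after dosing has ended.

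**Working it through.** **1. Is early baseline testing really open?** Nothing else in the plan sets a floor. The reminder call before Visit 3 is optional (Section 6.2). The telephone screen is timed backward from the coming visit, not forward from the LP: "COVID symptom and exposure assessment 24-72 hours prior to study visits". A call at 24 hours is compatible with a visit the day after the LP.

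**2. Permitted interval from LP to battery.** Inputs: the Section 6.9 windows, counting Visit 3a as a return visit on day 1 or later.

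| Interval after the LP | Baseline (Visit 3a) | Post-treatment (Visit 8) |
|---|---|---|
| Days 1-6 | permitted (6 days) | excluded |
| Days 7-14 | permitted (8 days) | permitted (8 days) |
| Days 15-30 | permitted (16 days) | excluded |

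Check: 6 + 8 + 16 = 30. A baseline on days 1-6 is closer to an LP than Visit 8 can be, so an after-effect would push the change toward improvement. A baseline on days 15-30 is farther from an LP than Visit 8 can be, so an after-effect lasting past day 7 would push the change toward decline. These are counts of permitted days, not of participants. The documents do not say when Visit 3a is usually held.

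**3. Outcomes outside the problem.** The baseline CDR is taken at Visit 1, before any LP. The footnote to Section 6.9 says "CDR will only be repeated at visit 4 if visit 1 was conducted more than 60 days prior". A repeat therefore needs at least 61 days from Visit 1 to Visit 4. Visit 2 is at most 30 days after Visit 1, so the repeat falls at least 61 − 30 = 31 days after the first LP. The primary CSF outcome and the Aim 3 samples are collected at the LP visits themselves and do not depend on the interval to the battery.

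**4. The twelve-week label (84 days).** Inputs: first dose at Visit 4 (Section 5.2), taken as day 0, and the windows in Section 6.9.

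- Visit 4 to Visit 7: 28 + 21 + 7 = 56 days. With ±2 days at each of three visits, 56 ± 6 = 50 to 62.
- Visit 8 from first dose, nominal: 56 + 7 = 63 to 56 + 14 = 70.
- With the 56 ± 3 days of Section 1.4: 53 + 7 = 60 to 59 + 14 = 73.
- With cumulative windows: 50 + 7 = 57 to 62 + 14 = 76.
- Visit 8 from last dose: 7 to 14 days.

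The scheduled windows do not give 84 days from either the first or the last dose. Counted from Visit 3a, which is 0-15 days before Visit 4, the range is 57 to 76 + 15 = 91 days and does include 84, but no section names that starting point. Under Section 5.5, dosing stops around each COVID-19 vaccine injection for 4 + 3 = 7 days, or 8 counting the injection day, and the investigators may extend study time. With one injection the range becomes 57 + 7 = 64 to 76 + 8 = 84. With two it becomes 57 + 14 = 71 to 76 + 16 = 92.

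**The case against.** Three arguments on the other side carry weight.

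First, a reader might infer that the design biases Aim 4 toward improvement. The documents do not support that. More of the permitted baseline days lie farther from an LP than Visit 8 can (16) than lie closer (6), and Section 3.3 itself names a persistent form of headache. The shift toward improvement is confined to participants tested on days 1-6. For those tested on days 15-30 the possible error runs the other way. This objection stands, and it rules out any claim about net direction.

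Second, a reader might want the bias put in standard deviations. The documents give no rate of LP after-effects, no effect of them on scores and no distribution of Visit 3a dates. Any figure would rest on invented inputs, so none is given.

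Third, the plan already has partial safeguards. Visit 3a includes an adverse event review, a medication review and a reassessment of willingness, and the 30-day window leaves room to postpone a symptomatic participant. These would help identify affected cases, but no rule requires postponement and Section 7.2 does not use the information. The objection lowers the stakes but does not remove the gap.

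On the label, it is tempting to say that Visit 8 can never fall 12 weeks after the first dose, or that its timing is undefined. Neither holds. A discretionary extension for vaccination can bring day 84 within reach, and the sentence carrying the label also fixes the visit at 7-14 days after the LP. No analysis relies on the twelve weeks. Section 1.4 speaks of "a post-intervention visit for study outcomes on final day of dosing and up to +14 days", which can be read as covering Visits 7 and 8 together. In Section 6.7, the instruction that times Visit 8 from itself is a slip that the next heading corrects.

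**Conclusion.** The concern holds as a minor design gap. Baseline testing within a week of an LP is permitted and post-treatment testing within a week of one is not, in a single-arm pre/post comparison with no planned check on that interval. Early testing is possible, not shown to occur. If it occurs, and if LP after-effects lower scores, the change for those participants is shifted toward apparent improvement. The overall effect on Aim 4 has unknown direction and size.

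This rests on reading the Section 6.3 and 6.9 windows as written and on the protocol's own list of LP risks. Severity is limited because Aim 4 is a secondary outcome in a feasibility-sized pilot, and because the missing minimum does not touch the primary outcome, Aim 3 or the baseline CDR. The twelve-week label is a wording matter and would not merit a comment alone.

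**What to change.** 1. In Sections 6.3 and 6.9, set the Visit 3a window to 7-30 days after Visit 2, using the minimum the protocol already applies at Visit 8. This adds no visit or test and keeps 24 of the 30 permitted days. If the 30-day limit on the whole baseline period in Section 1.4 is enforced, 30 − 7 = 23 days remain for the other baseline steps. The windows stay unequal above the minimum (7-30 against 7-14 days), so the possible error from baselines on days 15-30 remains. Matching them fully at 7-14 days would leave only 8 of 30 days.

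2. If baseline visits are already done, report each participant's interval from LP to battery at both occasions, and add a summary of Aim 4 that leaves out baseline intervals under 7 days. The visit dates needed are already collected. The cost is lost participants: if two of 10 were tested early, 8 remain. The summary is therefore descriptive only.

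3. Reconcile the twelve-week wording in Section 6.8 with the scheduled timing, and align Sections 1.4, 3.1, 3.2 and 6.7 with it. Report Aim 4 as change measured 1-2 weeks after the end of the 8-week course: nominally day 63-70 from first dose, 57-76 with cumulative windows, and later only if dosing is extended for vaccination. This is wording only.

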6.9. Summary Visit Schedule Table

Visit Number	Visit 1 MCD	Visit 2 MCD	Visit 3a MCD	Visit 3b MCD	Visit 4 MCD	Visit 5 MCD	Visit 6 MCD	Visit 7 MCD	Visit 8 MCD
Visit Window		V1 + up to 30d	V2 + up to 30d	w/in 24- 72 hrs of Visit 4	V3 + up to 15d	V4 +4w ±2d	V5 +3w ±2d	V6 +1w ±2d	V7+7- 14d

Consent	Х								
Reassess willingness to participate		X	Х		х	Х	Х	Х	Х
CDR	Х				X***				Х
Vitals: BP,HR,T,RR, Pulse Oximetry	Х	X	Х		X	Х	Х	Х	Х
Height	Х								
Weight	Х				X	Х	Х		Х
Has & P	Х								Х
ConMeds	Х	X	X		X	Х	Х	X	Х
AE Review		X	X		X	Х	Х	X	Х
		Bl	ood Drav	vs, Labs, a	and Lumb	ar Punctu	ires		
COVID-19 RT- PCR swab**				X					
$I \subset I \cup I \cup I \cup I \cup I$									
Fasting Blood Draw		X			X	Х	X	X	Х
Fasting Blood Draw Non-fasting Blood Draw	X	X			X	Х	Х	X	Х
Fasting Blood Draw Non-fasting Blood Draw CBC w diff	X X	X			X X	X X	X X	X	X X
Fasting Blood Draw Non-fasting Blood Draw CBC w diff CMP with lipid panel	X X X	X			X X X X	X X X	X X X	X	X X X
Fasting Blood Draw Non-fasting Blood Draw CBC w diff CMP with lipid panel Hemoglobin A1c	X X X X	X			X X X X X	X X X	X X X	X	X X X X
Fasting Blood Draw Non-fasting Blood Draw CBC w diff CMP with lipid panel Hemoglobin A1c	X X X X X X	X			X X X X X	X X X	X X X X	X	X X X X
Fasting Blood Draw Non-fasting Blood Draw CBC w diff CMP with lipid panel Hemoglobin A1c PT/PTT/INR Routine Urinalysis	X X X X X X X	X			X X X X X X	X X X	X X X X X X	X	X X X X X
Fasting Blood Draw Non-fasting Blood Draw CBC w diff CMP with lipid panel Hemoglobin A1c PT/PTT/INR Routine Urinalysis Research Labs	X X X X X X X	X X X			X X X X X X	X X X	X X X X X	X X X	X X X X X

Cognitive, Physical, and Sensory Assessments								
Snack Provision (optional)	Х						Х	Х
MoCA		Х						Х
HVLT-R		Х						Х
Craft Stories		Х						Х
Benson Figure		Х						Х
Number Span Test		Х						Х
Trail Making Test A&B		Х						Х
Phonemic and Semantic Fluency		Х						Х
MINT		Х						Х
Hayling		Х						Х
GDS		Х						Х
FAQ		Х						Х
NPI		Х						Х
Electronic Gait Mapping		Х						Х
Grip strength		Х						Х
Study Medication								
Compliance Review					Х	Х	Х	
Administer in clinic							X*	
Dispense Study Drug				Х	X			

Schedule/Confirm Next Visit	X	X	Х		X	X	X	Х	
**COVID-19 symptom and exposure telephone assessment	X	X	Х	X	Х	Х	Х	Х	
End of Study									
Final AE review									Х
Final Forms Review									Х
Follow up instruction									X
Disenrollment Note									Х

**COVID testing 24-72 hours prior to drug dispensing visit; COVID symptom and exposure assessment 24-72 hours prior to study visits; COVID testing may be repeated in event participant shows signs or symptoms of COVID-19 or, if positive, until a negative test is achieved

*At visit 7, all remaining supply of RAPA should be returned to the study staff for a final drug accountability check.

***CDR will only be repeated at visit 4 if visit 1 was conducted more than 60 days prior.

7. Statistical Plan

7.1. Sample Size Determination

This is a pilot study to collect data on brain penetrance of a study medication. The sample size was determined as what would be feasible given the time and budget constraints of the pilot (i.e., one-year and \$50K).

7.2. Statistical Methods

Analytical Approach.

Similar to an early phase 2 trial, we seek preliminary evidence of drug safety and tolerability with estimation of pre/post differences in a pertinent laboratory values and adverse event occurrences. We will report changes in post-intervention laboratory values relative baseline with the 95% confidence interval. Experimental results will be expressed as means \pm SE. Comparisons of means between pre/post evaluations will be done by regression using the intent to treat principle defined above. Given the small sample size, there are no plans for interim analyses.

8. Safety and Adverse Events

8.1. Definitions

Unanticipated Problems Involving Risk to Subjects or Others (UPIRSO)

Any incident, experience, or outcome that meets all of the following criteria:

- Unexpected in nature, severity, or frequency (i.e. not described in study-related documents such as the IRB-approved protocol or consent form, the investigators brochure, etc.)
- Related or possibly related to participation in the research (i.e. possibly related means there is a reasonable possibility that the incident experience, or outcome may have been caused by the procedures involved in the research)

• Suggests that the research places subjects or others at greater risk of harm (including physical, psychological, economic, or social harm).

Adverse Event (AE)

In general, AE is used very broadly and encompasses physical and psychological harms and includes: Any untoward or unfavorable medical occurrence in a human subject, including any abnormal sign (for example, abnormal physical exam or laboratory finding), symptom, or disease, temporally associated with the subject's participation in the research, whether or not it is considered related to the subject's participation in the research.

Intercurrent illnesses or injuries should be regarded as adverse events. Abnormal results of diagnostic procedures are considered to be adverse events if the abnormality:

- results in study withdrawal
- is associated with a serious adverse event
- is associated with clinical signs or symptoms
- leads to additional treatment or to further diagnostic tests
- is considered by the investigator to be of clinical significance

Serious Adverse Event (SAE)

Adverse events are classified as serious or non-serious. A serious adverse event is any AE that:

- results in death;
- is life-threatening (places the subject at immediate risk of death from the event as it occurred);
- results in inpatient hospitalization or prolongation of existing hospitalization;
- results in a persistent or significant disability/incapacity;
- results in a congenital anomaly/birth defect; or
- based upon appropriate medical judgment, may jeopardize the subject's health and may require medical or surgical intervention to prevent one of the other outcomes listed in this definition (examples of such events include allergic bronchospasm requiring intensive treatment in the emergency room or at home, blood dyscrasias or convulsions that do not result in inpatient hospitalization, or the development of drug dependency or drug abuse).

Adverse Event Reporting Period

The study period during which adverse events must be reported is normally defined as the period from the initiation of any study procedures to the end of the study treatment follow-up. For this study, the study treatment follow-up is defined as up to 2 weeks following the last administration of study treatment or procedures.

Pre-existing Condition

A preexisting condition is one that is present at the start of the study. A pre-existing condition should be recorded as an adverse event if the frequency, intensity, or the character of the condition worsens during the study period.

General Physical Examination Findings

At screening, any clinically significant abnormality should be recorded as a preexisting condition. At the end of the study, any new clinically significant findings/abnormalities that meet the definition of an adverse event must also be recorded and documented as an adverse event.

Abnormal Laboratory Values

Page 22

A clinical laboratory abnormality should be documented as an adverse event if any one of the following conditions is met:

- The laboratory abnormality is not otherwise refuted by a repeat test to confirm the abnormality
- The abnormality suggests a disease and/or organ toxicity
- The abnormality is of a degree that requires active management; e.g. change of dose, discontinuation of the drug, more frequent follow-up assessments, further diagnostic investigation, etc.

Hospitalization, Prolonged Hospitalization or Surgery

Any adverse event that results in hospitalization or prolonged hospitalization should be documented and reported as a SAE unless specifically instructed otherwise in this protocol. Any condition responsible for surgery should be documented as an AE if the condition meets the criteria for and adverse event.

Neither the condition, hospitalization, prolonged hospitalization, nor surgery are reported as an AE in the following circumstances:

- Hospitalization or prolonged hospitalization for diagnostic or elective surgical procedures for a preexisting condition.
- Surgery should not be reported as an outcome of an adverse event if the purpose of the surgery was elective or diagnostic and the outcome was uneventful.
- Hospitalization or prolonged hospitalization required to allow efficacy measurement for the study.
- Hospitalization or prolonged hospitalization for therapy of the target disease of the study, unless it is a worsening or increase in frequency of hospital admissions as judged by the clinical investigator.

